## Protocol Synopsis

**Study title.** Direct Acting Antiviral Effects on the Liver (deLIVER Study)

**NCT number:** NCT02938013

**IND number:** 132393

**Study phase:** Phase 3b

**Study Design:** Open-label, partially-randomized plasma and liver sampling study to assess HCV kinetics during treatment with two (Sofosbuvir/Velpatasvir) or three (Sofosbuvir/Velpatasvir/Voxilaprevir) direct acting antivirals (DAAs)

Cohort 1: Paired liver biopsies on Day 0 and Day 7

Antiretroviral therapy (HIV seropositive only)													
Step 1	Step 2								Step 3			Step 4	
Screening/ Randomization	SOF/VEL/VOX or SOF/VEL								SOF/VEL			Follow-up	
	Entry/D0	D1	D2	D3	D4	D5	D6	D7	WK4	WK8	WK12	WK16	WK24
	Liver BX	VK	VK	VK	VK			Liver BX	VK	VK	VK	VK	VK
	VK							VK					

Cohort 2: Paired liver biopsies on Day 0 and Day 4

Antiretroviral therapy (HIV seropositive only)													
Step 1	Step 2								Step 3			Step 4	
Screening/ Randomization	SOF/VEL/VOX or SOF/VEL								SOF/VEL			Follow-up	
	Entry/D0	D1	D2	D3	D4	D5	D6	D7	WK4	WK8	WK12	WK16	WK24
	Liver BX	VK	VK	VK	Liver BX			VK	VK	VK	VK	VK	VK
	VK												

VK, viral kinetics; BX, biopsy; SOF, sofosbuvir; VEL, velpatasvir; VOX, voxilaprevir; D; day; WK, week.

**Study duration:**

Step 1	Screening/ Randomization , up to 42 days (6 weeks)
Step 2	Paired liver biopsy for intrahepatic HCV dynamics , 7 days (1 week); intensive viral kinetics (VK) plasma and liver assessment
Step 3	HCV treatment , 77 days (11 weeks); continuation treatment with two DAAs (Sofosbuvir/Velpatasvir)
Step 4	Post-treatment follow up, 84 days (12 weeks)
Total	Up to 30 weeks

**Sample size:** 15 participants (up to 20 screened to account for screen failures)

**Population:** Adults ages ≥ 18 years to ≤70 years with HCV genotype 1a infection with no cirrhosis and no prior HCV treatment (treatment naïve). Five participants with HIV infection taking protocol-specified antiretroviral therapy and ten participants without HIV infection.

**Cohort assignment:** Nine subjects will be assigned to Cohort 1 as follows: 3 subjects in Arm A, 3 subjects in Arm B, and 3 subjects in Arm C. The subsequent six subjects will be enrolled into Cohort 2 as follows: 2 subjects in Arm A, 2 subjects in Arm B, and 2 subjects in Arm C.

## Abstract

Treatment of chronic hepatitis C virus infection with direct acting antivirals (DAAs) is highly effective in persons with and without HIV infection when administered for durations of at least 12 weeks. Shorter durations of treatment are associated with viral persistence in the liver and post-treatment relapse in some but not all patients. In general, measurement of the magnitude and rapidity of the viral kinetic response in the blood is not predictive of persistence of the virus in the liver, leading to post-treatment relapse. Little is known about the role of the intrahepatic viral kinetic during antiviral treatment or about the contribution of the patient immune system in control of the virus within the liver. In addition, the potential contribution of an additional antiviral with a different mechanism of action to intensify viral clearance of the liver has not been evaluated. The present study will assess the viral kinetic response in the plasma and the liver of 15 individuals randomized to treatment with two or three direct acting antivirals over a one week dosing period. All participants will undergo core needle liver biopsy at entry/day 0 prior to taking antivirals and on treatment day 7 (cohort 1) or treatment day 4 (cohort 2) to assess intrahepatic viral kinetics using the technique of single cell laser microdissection. To examine the role of HIV coinfection on viral kinetics, patients with HCV genotype 1a with and without HIV coinfection will be enrolled; to minimize heterogeneity, all HIV-infected patients will be required to be receiving protocol-specified antiretrovirals. The effect of HIV infection will be examined by comparison of the plasma and liver viral kinetics in 5 patients with HIV/HCV and 5 participants with HCV alone treated with the combination of two oral antivirals for 7 days. The effect of the addition of a third antiviral which inhibits HCV NS3/4A protease to the standard treatment with two antivirals which inhibit HCV NS5A and NS5B will be examined by randomizing patients with HCV mono-infection to treatment with two or three DAA over a 7 day period to assess plasma and liver viral kinetics. All participants will be offered standard of care treatment with two antivirals for an additional 11 weeks to complete a 12 week treatment course and will be followed for 12 weeks after stopping treatment to determine HCV treatment outcome.

## 1.0 Hypothesis

Hepatitis C virus (HCV) cure, sustained virologic response (SVR) is the consequence of the clearance of non-uniform clusters of HCV-infected cells and a decrease of intracellular HCV RNA per infected cell, which are in turn modified by the associated intrahepatic immune response in the first week of therapy in subjects with HCV with and without HIV coinfection.

2.1 One week after treatment with direct-acting antivirals, the decline in intrahepatic and intracellular HCV RNA will be greater in patients treated with an NS3 protease inhibitor in combination with inhibitors of NS5A and NS5B compared to those treated with the latter two inhibitors alone.

2.2 One week after treatment with direct-acting antivirals, the decline in intrahepatic and intracellular HCV RNA quantity will be greater in persons with HCV compared to those with HIV/HCV coinfection.

## 2.0 Objectives

**3.1 Primary Objective:** The primary objective is to estimate the 1-week change in the proportion of HCV-infected hepatocytes in participants with HCV mono-infection and HIV/HCV coinfection on therapy with two or three DAAs with different mechanisms of action using single cell laser microdissection (scLCM).

### 3.2 Secondary Objectives:

3.2.1. Estimate the change over the first week in plasma HCV RNA in subjects with HCV mono-infected and HIV/HCV co-infected participants on therapy with two or three DAAs

3.2.2. Estimate the 1 week change in the amount of HCV RNA per infected hepatocyte using scLCM on liver biopsy specimens, obtained just prior to treatment initiation (pre-treatment), and after the first week of DAA therapy.

3.2.3. Estimate the change in the proportion of HCV-infected hepatocytes that express interferon-stimulated genes (ISGs) within the first week of DAA therapy using scLCM.

3.2.4. Measure the change in expression of ISGs in non-parenchymal intrahepatic immune cells (Kupffer cells, plasmacytoid dendritic cells) within the first week of DAA therapy using scLCM.

### 3.3 Exploratory Objectives:

3.3.1. Estimate the 1 week change in expression of ISGs from peripheral blood mononucleated cells (PBMCs) within the first week of DAA+RBV therapy using scLCM.

3.3.2. Compare sequence(s) of HCV protease, nonstructural protein 5A (NS5A), and nonstructural protein 5B (NS5B) depending on the peripheral sequence) of intrahepatic HCV RNA in single cells and bulk tissue, before and during week 1 of DAA+RBV therapy.

3.3.3. Estimate the week 1 change in the sizes and numbers of HCV-infected clusters on DAA therapy to test whether clearance of HCV-infected hepatocytes occurs in spatially random patterns or within specific clusters.

## 3.0 Background

### 4.1 Disease Under Study

HIV infects approximately 30 million people worldwide and more than 1 million people in the US [1]. While antiretroviral therapy (ART) has dramatically decreased AIDS-related mortality, people living with HIV (PLWH) still have higher mortality than uninfected people. Liver-related mortality has consistently been found to be among the leading causes of death in PLWH in the US during the ART era, and HCV coinfection disproportionately contributes to liver disease in this population [2, 3]. Because of common routes of transmission, between 25-80% of PLWH in the US have been reported to be coinfecting with HCV [4]. HIV worsens HCV in several ways: i) by decreasing the likelihood of spontaneous clearance; ii) by increasing the HCV RNA level, iii) by accelerating the progression of HCV-related liver disease; and iv) by worsening the response of HCV to interferon (IFN)-based treatments [4]. Improved HCV therapies have reduced the gaps in efficacy between HCV mono-infected persons and HIV/HCV co-infected persons when given for standard durations of 12 weeks; however, whereas shortened therapy has delivered promising results for HCV mono-infected persons, they have been disappointing for HIV/HCV co-infected persons.

HCV chiefly replicates in liver hepatocytes: HCV eradication is the primary clinical outcome in HCV treatment, a composite phenomenon that reflects the suppression of new hepatocyte infections and the clearance of already infected hepatocytes. There has been rapid growth in the development of DAAs that target the intracellular lifecycle of HCV to suppress viral replication, i.e., new hepatocyte infections. In combination, DAAs have few side effects and deliver high rates of SVR. However, questions remain about the biology of HCV clearance and how it is impacted by treatment duration. Since, conceptually, duration of therapy hinges upon suppressing viral replication for sufficient time to allow host clearance of HCV-infected hepatocytes, combination DAA therapy is anticipated to result in complete suppression of HCV replication that will permit accurate measurements of the rate of clearance of HCV-infected hepatocytes. In addition, host clearance of HCV-infected hepatocytes is largely presumed to be due to the immune response; therefore, studies linking host immunity with the rate of clearance of HCV-infected hepatocytes in a situation without IFN may underscore mechanisms that can be targeted to shorten therapy in the future.

A major challenge in mechanistic studies of HIV/HCV coinfection is the absence of a representative animal model. In addition, *in situ* studies of human HCV infection have been difficult to develop due to technical hurdles. We have optimized a technique that integrates a narrowly focused laser with a fully automated light microscope (laser capture microdissection; LCM) to study single hepatocytes in the HCV-infected liver. Our team used scLCM to quantify the proportion of infected hepatocytes in subjects with chronic HCV, and we found that between 21-45% of hepatocytes were HCV-infected [5]. Our data are consistent with earlier studies of *in situ* HCV infection, but with the added advantage that host mRNA can be quantified in the same cells. Pal et al. used *in situ* hybridization to identify that approximately 40% of hepatocytes had HCV RNA [6]. Similarly, Liang et al. used 2-photon excitation of Q-dot probes to detect hepatic HCV antigens and RNA, reporting that between 1.7-21.6% of hepatocytes are infected [7]. Furthermore, because scLCM permits study of host gene expression, it can be employed to quantify immune responses to HCV and metabolic responses to study drugs. scLCM, therefore, is a validated measure to study HCV infection in human liver tissue, and could feasibly be applied to the study of HCV clearance with combination DAA therapy.

#### 4.2 Combination DAA Therapy

*Sofosbuvir/Velpatasvir (SOF/VEL)*. Sofosbuvir is an oral, nucleotide analogue inhibitor of HCV NS5B polymerase with demonstrated, potent antiviral activity in vitro and in vivo against HCV genotype 1, 2, 3, 4, 5, and 6 (pan-genotypic). SOF was approved by the US Food and Drug Administration (FDA) in October 2013 and is widely available across the world including as a generic agent manufactured in India. Velpatasvir (VEL) is an oral, second generation inhibitor of HCV NS5A with demonstrated potent antiviral activity in vitro and in vivo against HCV genotype 1, 2, 3, 4, 5, and 6 (pan-genotypic). VEL was evaluated with SOF as a fixed-dose combination (FDC) tablet (SOF 400 mg/VEL 100mg) taken by mouth once daily for 12 weeks in four clinical trials (ASTRAL-1, 2, 3, and 5) which included participants with HCV genotype 1, 2, 3, 4, 5, and 6 with HIV co-infection (ASTRAL-5) and among HCV mono-infection (ASTRAL 1, 2, 3) with and without compensated cirrhosis. The regimen evaluated was interferon- and RBV-free. Of note, ASTRAL-4 tested SOF/VEL in participants with decompensated cirrhosis (Child-Turcotte-Pugh classification B, CTP B); patients with CTP B or C are excluded from the present study. Overall, the efficacy of SOF/VEL was high with SVR12 observed in 95-99% of participants (Table 1). In ASTRAL 1, 2, and 3, no HCV relapse was observed between the post-treatment week 12 (SVR12) and post-treatment week 24 (SVR24) which is consistent with HCV eradication or cure. In the ASTRAL-1 (HCV genotype 1, 2, 4, 5, 6) study, SOF/VEL was compared to placebo tablets (delayed treatment group) in a double-blind manner. Importantly, no difference in safety and tolerability was observed between SOF/VEL and placebo with respect to the quantity and quality of reported AEs and observed laboratory abnormalities in ASTRAL 1 that compared SOF/VEL to a placebo. In the ASTRAL-2 (HCV genotype 2) and 3 (HCV genotype 3) studies, SOF/VEL was compared to SOF + RBV in randomized controlled trials. SOF/VEL was superior to SOF + RBV with respect to SVR12 (efficacy) as well as safety

and tolerability. In pooled analyses of data of participants from ASTRAL 1, 2 and 3, the overall efficacy was estimated at 98%.

**Table 1. Summary of SVR results from ASTRAL-1, 2, 3 and 5**

	SVR 12 (95 confidence interval)			
	ASTRAL-1	ASTRAL-2	ASTRAL-3	ASTRAL-5*
N	624	266	552	106
Overall	99 (98, >99)	99 (96, 100)	95 (92, 98)	95
Genotype				
1a	98.1 (95.2, 100)			95
1b	98.5 (96.5, 99.5)			92
2	100 (96.5, 100)	99 (96, 100)		100
3				92
3a			95.5 (90.9, 100)	
3b			100 (15.8, 100)	
3h			0	
3k			100 (2.5, 100)	
3 (no subtype confirmed)			88.9 (51.8, 99.7)	
4	100 (96.9, 100)			100
5	97.2 (85.1, 99.9)			
6	100 (91.4, 100)			
Disease				
No cirrhosis	99 (97.7, 99.7)		97 (93.5, 98.9)	94
Cirrhosis	99.2 (95.5, 100)		91.3 (82.8, 96.4)	100
Prior Treatment				
Naive	98.8 (97.3, 99.7)		97.1 (93.8, 98.9)	93
Experienced	99.5 (97.3, 99.6)		90.1 (80.7, 95.9)	97

In the United States and Europe, this regimen is commercially available as a fixed-dose combination tablet that includes the nucleotide HCV NS5B inhibitor, sofosbuvir 400 mg and the HCV NS5A inhibitor, velpatasvir 100 mg. For persons with compensated liver disease, this combination is approved in the United States for the treatment of chronic HCV genotype 1, 2, 3, 4, 5, and 6 as a single tablet taken by mouth once daily with or without food for 12 weeks. The brand name of this combination product is Epclusa®.

*Sofosbuvir/Velpatasvir/Voxilaprevir (SOF/VEL/VOX).* Voxilaprevir, previously known as GS-9857, is an inhibitor of HCV NS3/4A protease. In vitro, sofosbuvir, VEL, and VOX alone displayed potent inhibition against HCV genotype 1a, 1b, 2a, 2b, 3a, 4a, 5a, 6a, and 6e, and the combination of SOF and VOX SOF and VEL, or VOX and VEL demonstrated additive to slightly synergistic activity across multiple genotypes. In vitro cross-resistance studies showed no cross resistance of SOF, VEL, and VOX. SOF/VEL/VOX is therefore expected to have an improved resistance profile compared with the individual agents. This three DAA combination has been evaluated in phase 2 clinical trials and larger phase 3 clinical trials are underway. The contribution of the HCV NS3 protease inhibitor, VOX, to the hepatic clearance of HCV is of particular interest in that the addition

[figure not shown]
of a DAA with a different mechanism of action to SOF/VEL may prevent to persistence of viral variants with resistance associated polymorphisms which may confer decreased susceptibility to the HCV NS5A inhibitor, VEL and/or the NS5B inhibitor, SOF.

In addition, inhibition of the HCV protease may restore innate intra-hepatic immune functions that are thought to be impaired by the virus. In response to viral replication intermediates, such as viral RNA and proteins, IPS-1 and TRIF adaptor protein act as signaling intermediates in retinoic acid-inducible gene (RIG-I) and/or Toll-like receptor 3 (TLR3) pathways. Activation of these pathways induces IRF3 activation and subsequent transcriptional activation of type I interferons (IFN- $\alpha/\beta$ ) and interferon-sensitive genes (ISGs). Type I interferons and ISGs play a major role in combating viral infections. Cleavage of IPS-1 and TRIF by HCV NS3/4A blocks the downstream signaling pathway, resulting in inefficient activation of IRF3 and severely reducing the host innate immune response against the viral infection. It is possible that HCV protease inhibitors (PI) can play a dual role in countering viral infection through a direct antiviral mechanism, as well as by abrogating the HCV protease-mediated downregulation of innate immunity pathways, such as the RIG-I and TLR3 pathways.

The comparison of the intra-hepatic HCV kinetic and immunologic response after 7 days for dosing with SOF/VEL and SOF/VEL/VOX will permit the in vivo assessment of the role of protease inhibition on hepatic clearance of HCV during DAA treatment.

The change in the timing of the second biopsy is based on investigator review of unpublished, preliminary data from A5335s was presented at the Annual ACTG Network Meeting in June 2017. In this study, two participants with HIV/HCV coinfection underwent paired liver biopsies at day 0 and day 7 of treatment with paritaprevir/ritonavir/ombitasvir + dasabuvir. In both participants, the proportion of HCV-infected hepatocytes had decreased to only 1% (Figure 1). The rationale for the second liver biopsy at day 4 is that this earlier time point will allow better understanding of this rapid and profound reduction in HCV burden and allow for the more precise modeling of HCV elimination from the liver.

Figure 1: Proportion of HCV-infected hepatocytes at Day 0 and Day 7, A5335S

The vertical axis represents the number of HCV-infected hepatocytes counted by sLCM and the horizontal axis represents the HCV RNA production of each hepatocyte in IU/mL (one IU = two copies of HCV RNA) with zero (0) representing an uninfected hepatocyte.

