### 7.1 Step 1. Screening/ Randomization

Following informed written consent, participants will undergo screening procedures as per schedule of Events (Table 4).

The first nine subjects enrolled will be assigned to Cohort 1 as follows: 3 subjects in Arm A, 3 subjects in Arm B, and 3 subjects in Arm C. The subsequent six subjects will be enrolled into Cohort 2 as follows: 2 subjects in Arm A, 2 subjects in Arm B, and 2 subjects in Arm C.

Eligible participants who are coinfecting will be randomized before Entry/ Day 0. Randomization will occur for eligible monoinfected subjects with a 1:1 between SOF/VEL and SOF/VEL/VOX. Eligible subjects who are coinfecting will be non-randomly assigned to receive SOF/VEL. Subjects must enter Step 2 within 42 days of screening. Screening evaluations to determine eligibility must be completed within 42 days prior to entry, with the exception of IL28B, which can be pulled from historical records or performed during screening, and HCV genotype, which can be pulled from historical records up to 6 months before screening or performed at screening. Subjects may be rescreened at the PI's discretion. Laboratory parameters may be repeated as clinically necessary to be resulted within 30 days of Day 0 as required by Johns Hopkins.

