### 8.8 Liver Tissue preparation and intra-hepatic VK analysis

#### An outline of single cell Laser Capture Microdissection (scLCM)

To address the mechanisms underlying HCV clearance, we will use several novel techniques to measure the number and the distribution of HCV-infected hepatocytes, intracellular immune responses, and intrahepatic drug concentrations. Single hepatocytes will be separately analyzed for their HCV RNA content and innate immune responses by integrating scLCM and quantitative PCR (qPCR). We will employ four major methodological advances to study the clearance rate of HCV-infected hepatocytes during DAA treatment: i) scLCM, ii) high-resolution

qPCR, iii) unbiased sampling with an integrated image bank to map the viroscapes, and iv) single-cell HCV Core-E1 sequencing.

**Tissue preparation.** Liver tissue is processed and placed on glass and polyethylene naphthalate (PEN) membrane slides while being kept at  $-24^{\circ}\text{C}$  for the duration of their pre-visualization time to preserve RNA. After staining, slides are stored at  $-80^{\circ}\text{C}$  until scLCM. RNase inhibitors such as RNeasy Protect are avoided as their high viscosity impedes scLCM.

**scLCM.** A Leica LMD 6500, laser microdissection system, was acquired by [name]. The instrument integrates a high-density photon laser with a fully motorized light microscope. Since bulk tissue analysis pools disparate signals, and tissue disruption with cell purification neglects anatomic context, conventional microdissection was developed to enrich cells of a given type for downstream analysis. Previous studies have required hundreds to thousands of cells. We have improved the technique by dissecting individual liver cells into separate containers, developing scLCM through rigorous testing and validation using liver samples from HCV-infected subjects [5, 8].

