High-resolution qPCR permits interrogation of the same cells for multiple pieces of data and, importantly, allows for discarding of suboptimal data (defined by insufficient amounts of a housekeeping RNA). *In situ* scLCM has the advantage of finding natural and consequently relevant determinants of HCV replication. While other methods exist to enumerate HCV-infected hepatocytes, we are not aware of another team using LCM to quantify the burden of infection per cell, nor of comparing host RNAs in infected and uninfected cells.

*Unbiased sampling and integrated image bank mapping.* Initial attempts to identify and quantify HCV-infected hepatocytes *in situ* were based on prior immunohistochemical (IHC) staining for HCV proteins, followed by dissection of HCV+ hepatocytes. These attempts were impeded by inconsistent staining, hepatic autofluorescence, and RNA loss under conventional staining protocols. We have circumvented traditional approaches by separately isolating consecutive hepatocytes prior to determining whether they are infected [5]. Pre- and post-scLCM images are stored on a secure server. After high-resolution qPCR of coded scLCM samples, virtual maps of HCV infection are assembled using stored images. The advantage of this approach is that it leverages quantitative methods, rather than competing *in situ* methods, which are semi-quantitative or even qualitative, to reveal the peaks and nadirs of HCV replication in the liver, which we have termed the viral landscape, or viroscape. The quantitative viroscape is optimally conceived for modeling applications where qualitative approaches would be inadequate. The sampling is spatially unbiased, in that hepatocytes are collected consecutively in antiparallel grids, irrespective of whether they are infected. Infection of a given hepatocyte is only determined after processing each cell separately, and operators are blinded to positional maps until final analysis. Since the minority of hepatocytes is HCV-infected, unbiased sampling permits comparisons of intracellular signals between infected hepatocytes and adjacent uninfected hepatocytes that are presumably refractory to infection despite high HCV viral loads. A linked advantage to this approach is that, rather than committing full tissue sections to interrogation of a single or small number of host mRNA molecules, each scLCM-dissected cell can be separately interrogated for multiple signals.

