## 11.0 Statistical Analyses Plan:

All outcomes will be summarized and described with appropriate summary statistics. For example, estimated binomial proportions (e.g., for % of HCV-infected hepatocytes) will include 95% confidence intervals. Means, medians for continuous outcomes will include confidence

intervals and key percentiles (eg, 25th, 75th percentiles), respectively. Outcomes defined as changes will also present summary distribution of values at each time point contributing to change outcome. In addition, because of small sample size, outcomes will also be summarized on a per-subject basis for reporting. Changes will be defined as absolute differences for those outcomes where baseline distribution of proportion is close to 0 or 1, and relative (and absolute secondarily), changes otherwise. For continuous outcomes, both absolute and relative changes from baseline will be explored and summarized. Confidence intervals (using exact methods) on change outcomes will be calculated and presented.

For the primary outcome, the estimated differences will be summarized and described on a per-subject basis (i.e. 15 differences and intra-subject confidence intervals). Additionally, the proportion of infected hepatocytes will be summarized across subjects at each time point and presented. Finally, the average difference from week 0 to week 1 (absolute difference) for the study sample will be estimated and summarized.

For the plasma VK secondary outcome, longitudinal modeling will be used to combine plasma HCV viral loads (VL) over the first week. For instance, marginal modeling will focus on estimation of levels across the study sample (ie, population level inference). This can be used to describe the average change in HCV VL over the first week on treatment. In addition, (generalized linear) mixed effects models will focus on subject-specific inference (ie, prediction). Since this is a small study, these data will be graphically represented by subject.

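### The Day 4 biopsy is justified partly by modelling clearance from the liver, yet no liver analysis in Section 11 uses time to second biopsy, and the week 0 to week 1 average mixes Day 4 and Day 7 pairs

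*Combined protocol and SAP*

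**What the plan says.** **What the biopsies are for.** Section 4.2 (Combination DAA Therapy) explains the Day 4 biopsy by a rapid fall in infected hepatocytes seen in two participants of an earlier study. It gives two reasons: better understanding of that fall, and that the earlier time point will "allow for the more precise modeling of HCV elimination from the liver". Section 4.1 expects combination therapy to "permit accurate measurements of the rate of clearance of HCV-infected hepatocytes". Section 8.8 introduces the laboratory methods as a means "to study the clearance rate of HCV-infected hepatocytes during DAA treatment", and adds: "The quantitative viroscape is optimally conceived for modeling applications where qualitative approaches would be inadequate".

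**Design.** Section 7.1: "The first nine subjects enrolled will be assigned to Cohort 1 as follows", three per arm, with the second biopsy on Day 7. Then: "The subsequent six subjects will be enrolled into Cohort 2 as follows: 2 subjects in Arm A, 2 subjects in Arm B", and two in Arm C, with the second biopsy on Day 4.

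**Objective and analysis.** "The primary objective is to estimate the 1-week change in the proportion of HCV-infected hepatocytes" (primary objective). For the liver, Section 11 plans 15 per-participant differences with intervals, the proportion infected at each time point, and an average absolute difference from week 0 to week 1. Its general paragraph also provides for relative changes. Time enters a model only here: "For the plasma VK secondary outcome, longitudinal modeling will be used to combine plasma HCV viral loads (VL) over the first week".

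**The concern.** Sections 10 and 11 do not mention Day 4, do not use biopsy day as a variable and give no rule for combining the two cohorts. Two things follow.

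First, the modelling that partly justified the Day 4 timing has no counterpart among the planned analyses. If it is done later, the model, the handling of zero counts and the pooling of cohorts would be chosen after the data are seen, with five participants per group.

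Second, the one summary that is specified across participants treats every pair as a one-week pair. Two fifths of the pairs are Day 4 pairs. If infected cells continue to be lost between Day 4 and Day 7, the average is neither the 7-day nor the 4-day change, and as an estimate of the 7-day change it is too small.

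**Working it through.** **1. The plan's own precision figure (Section 10).** Inputs: proportion 0.50, 400 hepatocytes per participant and time point, five participants per group.

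- SE of one participant's difference = sqrt(2 × 0.5 × 0.5 / 400) = 0.0354 (plan: 0.035).
- SE of the mean of five = 0.0354 / sqrt(5) = 0.0158 (plan prints 0.015, a truncation).
- Half-width = 1.96 × 0.0158 = 0.031, as stated.

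The figure reproduces. It concerns a difference in proportions between baseline and week 1 and contains counting error only. No precision figure is given for a rate.

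**2. What the mixed average estimates.** Illustrative inputs: baseline p0 = 0.21 to 0.45 (four subjects described in Section 8.8) and p7 = 0.01 at Day 7 (Section 4.2: two participants, another regimen). Constant proportional loss is an assumption.

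Formulas: k = ln(p0/p7)/7; p4 = p0 × exp(−4k); mixed average = [3(p0 − p7) + 2(p0 − p4)]/5; shortfall = (p0 − p7) − mixed average = (2/5)(p4 − p7).

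| p0 | k per day | half-life, days | p4 | Day 4 change | Day 7 change | mixed average | shortfall |
|---|---|---|---|---|---|---|---|
| 0.21 | 0.435 | 1.59 | 0.037 | 0.173 | 0.200 | 0.189 | 0.011 |
| 0.45 | 0.544 | 1.27 | 0.051 | 0.399 | 0.440 | 0.424 | 0.016 |

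Against the half-width of 0.031, the shortfalls before rounding (0.0107 and 0.0164) are 0.35 and 0.53 of it. The mix is the same in the whole sample (6/15 = 2/5), so the shortfall is too.

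**3. Whether the planned data could give a rate.** With 400 independent cells per biopsy, one participant's k = ln(p0/pt)/t has approximate SE(k) = sqrt[(1 − p0)/(400 p0) + (1 − pt)/(400 pt)] / t.

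- Day 4 pair: 0.068 (p0 = 0.21) to 0.056 (p0 = 0.45) per day, from about 15 to 20 infected cells.
- Day 7 pair: 0.072 per day, from about 4 infected cells.

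Either pair gives an average rate with similar counting error, provided each is divided by its own elapsed time. Dividing a Day 4 pair by 7 would return 4/7 = 0.57 of its rate. These SEs are lower bounds: they omit between-participant variation, and Section 8.8 describes infected cells as clustered, so cells are unlikely to be independent.

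**4. Whether constant loss could be tested.** Compare k from two Day 4 with k from three Day 7 participants in one group. Take p0 = 0.33 (k about 0.50; SE(k) 0.060 and 0.072) and assume a between-participant SD of 0.10 per day.

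- SE of the difference = sqrt[(0.10² + 0.060²)/2 + (0.10² + 0.072²)/3] = 0.109 per day.
- 95% half-width on 3 degrees of freedom = 3.18 × 0.109 = 0.35 per day, against k of about 0.50.

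The comparison describes; it cannot verify the assumption.

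**The case against.** The strongest reply is that the plan does not need a rate. The primary objective is a one-week change, and no secondary or exploratory objective names a rate. The statements in Sections 4.1 and 8.8 are background and an introduction to laboratory methods. Only Section 4.2 links modelling to Day 4, and it gives a separate reason first that descriptive results can serve. The study is exploratory and was sized on feasibility. Section 11 already promises per-participant results, values at each time point and, where baseline is not near 0 or 1, relative changes. From these anyone can form pt/p0, and because Step 2 visits have no window (Section 7.2), the elapsed time is nearly fixed by cohort.

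Most of this stands. It limits the point to a secondary analysis and a clearer presentation. It does not rescue the average across participants: Section 11 specifies that as an absolute difference from week 0 to week 1, without separating the cohorts. Nor does it supply the modelling in Section 4.2, since relative change still ignores time.

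A further fair reply is that 1-week change may mean change within the first week. On that reading there is no shortfall from a 7-day target, but the average then combines changes over two different intervals and has no clear interpretation.

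**Conclusion.** The point holds in this form: the plan gives modelling of elimination as a reason for the Day 4 biopsies, specifies no liver analysis that uses time, and averages Day 4 and Day 7 pairs together. Under the illustrative inputs the average falls 0.011-0.016 short of the 7-day change, up to about half of the plan's stated half-width. That size depends on constant proportional loss, a 21-45% baseline and 1% at Day 7. The half-width used for comparison leaves out between-participant variation, so the shortfall would look smaller beside a realistic interval.

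Three stronger readings are tempting and are not supported:

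- A reader might infer that a loss rate is the quantity behind hypotheses 2.1 and 2.2. Both concern the decline in intrahepatic and intracellular HCV RNA after one week, which is a change at a fixed time.
- A reader might infer that the Day 4 biopsies can yield no rate. Each pair yields one under an assumed constant loss; the plan merely has no analysis that computes it.
- A reader might infer a large gain in precision over the current plan. Under the same inputs, the group SE of k is 24-31% lower with all five pairs than with the three Day 7 pairs alone, but nobody planned to use only three. Most of that gain is the step from three to five people: 1 − sqrt(3/5) = 22.5%.

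**What to change.** In Section 11:

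1. Report the planned absolute differences separately for Day 4 and Day 7, and do not label a mixture of the two as a week 0 to week 1 change.
2. Add a secondary, exploratory average loss rate per participant, k = ln(p0/pt)/t, with t the elapsed days from first dose to second biopsy. State the zero-count rule in advance (for example, adding 0.5 to a zero count), since only about four infected cells may be seen at Day 7.
3. Summarize k for Groups A, B and C with t-based intervals from between-participant variation, and also show it by cohort.
4. If a log-link model of infected-cell counts is preferred, include a participant-level slope or another allowance for between-participant variation. A model with group slopes only would rest on counting error and is not equivalent to step 3.

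The cost is about one paragraph of the analysis plan and little analysis time, with no new data or procedures. The downside should be stated in the plan: k is an average over the interval, and pooling Day 4 and Day 7 values assumes constant proportional loss. If the decline has two phases, the pooled value mixes different quantities. Two biopsies per person, and cohorts of two and three per group filled one after the other, can describe departures from constant loss but cannot test for them.
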